## 5) Procedures Involved\*

*Patients coming to the oculoplastic clinic who qualify for the study based on inclusion and exclusion criteria (With upper lid retraction or asymmetry>1mm) will have the study explained to them by a research study member and they can ask questions. They will receive information on risks and benefits to research participation. For interim analysis of futility, we will do the study with BT eye drops on first 10 patients and then evaluate the results to see if there are any significant effects. If clinically significant effects are seen, then 34 patients totally (17 in BT vs 17 in saline) are included. After a written consent is obtained, External Photographs will be taken by a standard camera in standardized room light. Eyelid measurements will be done including MRD1, MRD2, PF height with the eyes in the primary position. Tear meniscus height, Schirmer I test with anesthesia and ocular staining with fluorescein will be evaluated for all patients recruited before and after eye drops are installed by the PI or resident in the clinic in the eye with greater palpebral fissure height (one eye). In each visit all these data will be obtained again. The subjects will be allocated to the treatment based on the randomization sheet provided by the biostatics department that is handed to [name], Surgical Coordinator on the 4th who will inform the PI of the patient's number. After the PI sees the patient, she will inform the resident in the clinic. The resident or the fellow in the clinic will be asked to provide the PI with the eye drop (botulinum toxin A or saline in 1 cc syringes without needles) while not informing of the contents. The research team([name], [name], [name], [name]), also blinded to the study will gather the data and take the necessary photos (double Blinded).*

*Potential toxicity or life-threatening toxicity with topical botulinum toxin is unlikely.*

*Pressure on the lacrimal sac by the patients for 2 minutes will be done to minimize systemic absorption.*

*Patients will be provided a phone number to call if any complications occur.*

*BOTOX®, JEUVEAU, XEOMIN, and DYSPORT are Crystalline preparations of BT type A, FDA approved drugs for many indications including periocular wrinkles. Saline eye drops will be also used as placebo.*

*If any patient develops side effects that require a medical need to unblind and treat, the PI can find out which group was the patient allocated (unblinding) by contacting [name].*

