## **Number of Subjects**

10 Patient are recruited for interim analysis of futility. If significant, then 17 patients in each group (34 total) based on power calculations for alpha of 0.05 and power of 80% per the biostatistics department.

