## **Study Timelines**

Recruitment will occur for 1 year. After interim analysis, the study will end once 34 patients are recruited. The study length for the patient is expected to be at least 3 months, with the recruitment/baseline visit and follow up visits at 3 days, 1 week, 2 weeks, 1 and 3 months from the first visit, for a total of 6 visits. The study is expected to last about 1 year from the time of IRB approval to completion of all study activities, including analysis of identifiable data.

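### The step after the first 10 patients is called futility but continues only on a positive finding, under conflicting criteria with no outcome, visit or size, and with no control group

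*Combined protocol and SAP*

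**What the plan says.** Section 5) Procedures Involved introduces the step as futility: "For interim analysis of futility, we will do the study with BT eye drops on first 10 patients". All 10 receive toxin. The later, unnumbered Procedures Involved section confirms that randomisation to toxin or saline begins only after these 10.

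The condition for going on is worded three ways. Section 5 gives two of them in consecutive sentences: the team will "evaluate the results to see if there are any significant effects. If clinically significant effects are seen, then 34 patients totally" are to be included, 17 on toxin and 17 on saline. Number of Subjects says "10 Patient are recruited for interim analysis of futility. If significant, then 17 patients in each group". None of these sentences names an outcome, a visit, a size in mm, a test or an alpha for the step. The alpha of 0.05 and power of 80% in Number of Subjects are attached to the 17 v 17 comparison. Data Analysis names one test for the whole study, a paired t-test, and three domains: fissure height, ocular surface and tearing. Five post-baseline visits are planned.

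On selection, patients enter with upper lid retraction or asymmetry above 1 mm (section 4), and drops go "in the eye with greater palpebral fissure height (one eye". Study Timelines describes a schedule "with the recruitment/baseline visit and follow up visits at 3 days, 1 week, 2 weeks, 1 and 3 months from the first visit".

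**The concern.** A futility rule stops a study when a worthwhile effect has become implausible. This one stops unless an effect has been shown, so an inconclusive result in 10 patients would end the trial before any saline patient is enrolled. That makes it an efficacy hurdle, and the three wordings set it at different heights.

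The 10 patients have no control, so everything rests on a before-after change. The eye is chosen because it is the wider one. If the reading that selects it also serves as baseline, that reading is too high on average, and a later reading will tend to be lower even with an inert drop. The same step could therefore stop a drop that works or pass one that does not. It decides whether the randomised trial takes place at all.

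**Working it through.** **1. The plan's own figure.** Stated: 17 per group, alpha 0.05, power 80%. No effect size, SD or sidedness is given, so the number cannot be reproduced forwards. Solving backwards (two-sided, two-sample):
- Normal approximation: d = (1.960 + 0.842) × √(2/17) = 0.961.
- Noncentral t, 32 df: d = 0.991.
- At d = 1.0, 17 v 17 has 80.7% power.

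The design therefore implies an effect of about 1 SD.

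**2. The wordings can disagree on the same data.** For n = 10, t = mean fall / (SD/√10), with critical value 2.262 on 9 df.
- Mean fall 0.5 mm, SD 0.5 mm: t = 0.5/0.158 = 3.16, significant.
- Mean fall 1.0 mm, SD 1.5 mm: t = 1.0/0.474 = 2.11, not significant.

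Any clinical cut-off between 0.5 and 1.0 mm reverses both decisions. These values are illustrative.

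**3. The step read as two-sided P<0.05.** Assumptions: paired t-test, no change on saline, the 10 separate from the 34. Here d is the true mean change divided by its SD.
- Step: noncentrality d√10. At d = 1.0 the step is passed 80.3% of the time, so it stops wrongly 19.7% of the time.
- Final test: noncentrality d√(17/2), 32 df. At d = 1.0, 80.7%.
- Both: 0.803 × 0.807 = 0.648. At the back-solved d of about 0.99, 0.795 × 0.799 = 0.636.
- A true 1 mm fall with SD 1.5 mm (d = 0.667) is passed 47% of the time and stopped 53%.
- At d = 0.5 the step is passed 29% of the time and stopped 71%.

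Under the clinical wording there is no threshold to put into a formula, so no error rate exists to report.

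**4. Leaving visit and outcome open.** With no drug effect and no regression to the mean, a significant result in either direction at any of five visits occurs 16-19% of the time for one outcome. For three outcomes it is 39-47%. Correlations were assumed at 0.5-0.7 between visits and 0-0.3 between outcomes.

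**5. Regression to the mean.** The documents give neither reading error nor between-eye spread. Let e be the error SD of one fissure reading, s the SD of the true between-eye difference, and D the measured difference, with variance s² + 2e². If eyes are admitted at |D| > 1 mm, the wider one is treated, and the same reading is the baseline:

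expected fall = e²/(s² + 2e²) × E(|D| given |D| > 1 mm)

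- e = 0.3, s = 2: 0.05 mm.
- e = 0.5, s = 2 and s = 1: 0.13 and 0.28 mm.
- e = 0.7, s = 1: 0.45 mm.

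Simulating these cases for an inert drop, a P<0.05 step shows a significant fall in about 5% to 27% of series of 10, against 2.5% without regression.

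**6. A true futility rule.** Continue if mean fall + 1.383 × SD/√10 ≥ Δ, where Δ is the worthwhile reduction and 1.383 is the 90th percentile of t on 9 df. When the true fall equals Δ, the rule stops 10% of the time at any SD. At zero effect the chance of continuing is P(T ≥ −1.383), with T noncentral t, 9 df, noncentrality −√10 × Δ/SD:
- Δ = 1.0 mm: 4% at SD 1.0 mm, 23% at SD 1.5 mm.
- Δ = 0.7 mm: 20% and 45%.

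With Δ = 1 mm, a true fall of 0.7 mm (SD 0.7) is stopped 50% of the time, and 0.5 mm (SD 0.5) 96%. Both are 1.0 SD effects, which a P<0.05 step stops 20% of the time.

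**The case against.** The sentence that governs continuation uses the clinical wording, and the phrase in Number of Subjects may be shorthand for it. No test or alpha is attached to the step. A reader might infer that the plan runs at 65% power. The documents do not support that: the figure needs a P<0.05 test that the plan does not state for this step, and it needs the 10 to be separate from the 34, which the plan leaves open. Any pilot hurdle also lowers the overall chance of success, and using one is a legitimate design choice. This stands as a limit on the figures. It does not supply the missing criterion.

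A reader might also infer that regression to the mean will open the step or bias the trial's result. Neither is shown. The size rests on assumed error and spread, and it would be smaller for bilateral retraction without asymmetry. Recruitment Methods has eligibility assessed from the record at a routine visit, section 12 has a separate consent appointment, and section 5 takes study measurements after consent, so the qualifying and baseline readings may already differ. What remains is that the plan does not say which reading selects the eye. A false pass leads only to a saline-controlled comparison, where the same regression affects both randomised arms.

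Finally, 1 mm is tempting as the worthwhile reduction because it is the one lid measurement threshold in the plan. It is an entry criterion for asymmetry, not a treatment effect, and step 6 shows what it could cost.

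**Conclusion.** The point holds. A step labelled futility requires a positive finding in 10 uncontrolled patients, under wordings that can lead to opposite decisions, with no outcome, visit or size.

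The sizes are conditional. Read as a two-sided P<0.05 paired t-test, the step stops a 1.0 SD effect about 20% of the time. If in addition the 10 are separate from the 34 and saline shows no change, overall success is about 65% against the stated 80%. Under the clinical wording the error rate is unknown. A spurious fall of 0.05-0.45 mm is possible for reading error of 0.3-0.7 mm and between-eye SD of 1-2 mm, if the eye-choice reading is also the baseline. It is a threat to the go/no-go decision, not evidence of bias between the randomised arms.

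This should be corrected before the first 10 results are read, because the step decides whether randomisation happens.

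**What to change.** Replace the three phrases, in section 5 and in Number of Subjects, with one rule. The measure is palpebral fissure height (MRD1 + MRD2) of the treated eye at one named visit. Stop only if the upper one-sided 90% confidence limit for the mean reduction lies below a smallest worthwhile reduction. The sponsor states that reduction in advance, and it should be no larger than the effect assumed for 17 v 17. Do not default to the 1 mm entry threshold.

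Choose the eye on the qualifying reading from the routine clinic visit, and take baseline from a fresh reading at the separate consent appointment in section 12.

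The cost is protocol wording and one repeat lid measurement. The downside is that an ineffective drop goes on to randomisation more often than the 2.5% under a P<0.05 step: for a 1 mm threshold, about 4% at SD 1.0 mm and 23% at SD 1.5 mm, and more often with a smaller threshold. The false stop is about 10% only when the true effect equals the stated threshold. It is higher for smaller effects and lower for larger ones.

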## **Number of Subjects**

10 Patient are recruited for interim analysis of futility. If significant, then 17 patients in each group (34 total) based on power calculations for alpha of 0.05 and power of 80% per the biostatistics department.

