## Procedures Involved

**We anticipate that the procedures listed below will take about 30 to 40 minutes per patient. Each patient will have a complete ophthalmologic exam. Except as noted, the procedures below are not considered standard of care and are being conducted for the study alone.**

- A. Part 1: Pre-treatment data collection
  - External photographs, MRD1, MRD2, palpebral fissure height, tear meniscus height, Schirmer I test with anesthesia and ocular staining with fluorescein will be recorded.
- B. Part 2: Botulinum toxin or Placebo topical application
  - Subjects will be randomized to receive either 15 units of botulinum toxin A (BOTOX), incobotulinum toxin A (XEOMIN), prabotulinum toxin A (JEUVEA), the equivalent of 45 units of abobotulinum toxin A (DYSPORT) or balanced saline placebo in one eye after 10 patients are included for the interim analysis with BT eye drops topically on the surface of the eye
  - Then based on the randomization results, the examiner will apply botulinum eye drops or saline to the one of the subject's eyes.
- C. Part 3: Post-treatment data collection
  - Subjects will come back in 3 days, 1 week, 2 weeks, 1 & 3 months after they receive the treatment or control.
  - At each visit, subjects will have the measurements above again.
- D. Part 4: Data analysis
  - Data will be recorded and stored in a secure Microsoft Office Excel (Microsoft Corporation, Redmond, WA, U.S.A.) spreadsheet. Data will be graphically analyzed and represented with Adobe Photoshop (Adobe, Inc., San Jose, CA, U.S.A.).
  - Data assessed will involve assessing pre- and post-treatment MRD1 and MRD2, investigator-assessed measurements of ocular surface and tearing.
  - User performing analysis will be blinded to which eye received study drug.

Follow-up outside of the patient's next routine clinic visit will be needed for 3 days, 1 week, 2 weeks and 1 & 3 months. Patients who do have symptoms concerning any post-procedural complications will be instructed to notify study staff immediately. A phone number will be provided.

Outcomes Measures:

Primary outcome:

Outcome Measure Title: Change in palpebral fissure height

Outcome Measure Description: Palpebral fissure height will be calculated from the sum of marginal reflex distance 1 and 2 measured by the researcher.

Outcome Measure Timeframe: Baseline, day 3, 7, 14, 30 & day 90.

Secondary outcomes:

Outcome Measure Title: Change in eye ocular surface and tearing

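### The plan does not say whether the first 10 patients, all given BT before randomisation begins, count towards the 34; if they do, 10 of the 17 BT patients are unrandomised

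*Combined protocol and SAP*

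**What the plan says.** Section 5 (Procedures Involved) describes a first stage in which the team will "do the study with BT eye drops on first 10 patients and then evaluate the results to see if there are any significant effects". It continues: "If clinically significant effects are seen, then 34 patients totally (17 in BT vs 17 in saline) are included".

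Number of Subjects puts it this way: "10 Patient are recruited for interim analysis of futility. If significant, then 17 patients in each group (34 total". It ties 80% power at alpha 0.05 to that size. Study Timelines says "After interim analysis, the study will end once 34 patients are recruited".

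The later Procedures Involved section (Part 2) places randomisation to BT or saline "after 10 patients are included for the interim analysis with BT eye drops".

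On masking, section 5 hides the syringe contents from the principal investigator and the research team. Part 4 of the later section adds: "User performing analysis will be blinded to which eye received study drug". Section 5 also says that the drop goes "in the eye with greater palpebral fissure height (one eye".

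Data Analysis again gives 34 subjects and names a paired t-test. No section gives a total of 44, and none says whether the first 10 enter the final comparison.

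**The concern.** The single total of 34 can be read in two ways. Either 34 patients are randomised after a separate group of 10, or the 10 already occupy 10 of the 17 BT places.

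Under the second reading most of the BT arm was never randomised. Those 10 patients are earlier in time, have no concurrent controls, and stay in the trial only when their own results look favourable. Masking cannot protect their measurements, because everyone in that stage receives BT. Masking the analyst to the treated eye helps only in part: it does not hide that all 10 had BT, and the rule for choosing the eye means that the baseline fissure height points to it. The primary outcome is built from lid distances measured by the researcher, so knowledge of treatment could affect it.

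A team could adopt either reading without departing from the text, and could do so after seeing the first 10 results. The choice decides whether the trial's main comparison is randomised.

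**Working it through.** **1. The wording, side by side.**
- Towards counting the 10: section 5 calls them the first patients of the study, then gives 34 as the overall number. Both places call the look an interim analysis, which normally means a look at the trial's own data.
- Towards a separate group: Part 2 of the later Procedures Involved section starts randomisation after the 10. Number of Subjects and Study Timelines can be read as a sequence, the 10 first and then 34.
- Neither set of passages settles it.

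**2. Share of the BT arm if the 10 count.** 10/17 = 0.588, or 59%. That leaves 17 − 10 = 7 patients randomised to BT against 17 to saline.

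**3. The plan's own figure.** Inputs from Number of Subjects: alpha 0.05, power 80%, 17 per group. The effect size, SD, sidedness and test behind it are not given, so 17 cannot be reproduced directly. I assumed a two-sided two-sample t-test and solved for the standardised difference d that gives 80%.
- Power = P(|T| > t critical), where T is noncentral t with n1 + n2 − 2 degrees of freedom and noncentrality d × √(n1·n2/(n1 + n2)).
- For 17 v 17, √(289/34) = 2.915, and 80% power needs d = 0.991.

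**4. Bias if the 10 count.** Assume SD 1, no drug effect, and a shift s in the 10 only, from open-label measurement or period. The BT mean moves by (10 × s + 7 × 0)/17 = 0.588 × s.
- s = 0.2 gives 0.12 SD.
- s = 0.3 gives 0.18 SD.
- s = 0.5 gives 0.29 SD.

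This is before any selection on a favourable look.

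**5. False positives in BT's favour (nominal 2.5%).** The test is 17 v 17 with the 10 pooled into BT, by simulation. The plan gives no numerical go rule, so I assumed two: p < 0.05 in the favourable direction among the 10, or a mean of at least half the design effect (0.991/2 = 0.496 SD).

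| Shift in the 10 | If the trial always continued | Overall, after the go rule |
|---|---|---|
| 0.2 SD | 5.1% | 1.7% to 2.8% |
| 0.3 SD | 7.0% | 3.0% to 4.6% |
| 0.5 SD | 12.4% | 7.6% to about 10% |

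Among trials that continue, the rate is about 16% to 26% across these shifts. Much of that comes from selection alone. With no shift, the two rules let 2.5% and 5.9% of null trials continue, and 0.48% and 0.85% of all trials end as false positives. That is 0.0048/0.025 = 19% and 0.0085/0.059 = 14% of those that continue.

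**6. Power if the total stays at 34 and the 10 are set aside.** 34 − 10 = 24 are randomised. At 12 v 12 and d = 0.991, the noncentrality is 0.991 × √(144/24) = 2.43 with 22 degrees of freedom, and power is 64.1%. The normal approximation gives 65.3%. The one-sided versions give 66.4% (t) and 67.2% (normal). The standard error of the difference rises from √(2/17) = 0.343 to √(2/12) = 0.408 SD, a factor of 1.19 whatever the effect.

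**The case against.** The strongest reply is that the plan means 10 patients first and then 34 newly randomised. Three sections can be read that way, allocation follows a randomisation sheet from the biostatistics department, and the 80% is attached to 17 per group. Under that reading nothing is wrong with the comparison. This stands: the reading is legitimate and harmless. But no sentence adopts it, the number 44 never appears, and section 5 leans the other way.

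A second reply is that the go rule itself removes many false positives. This also stands. At a shift of 0.2 SD the overall rate is about nominal, and with no shift it is below nominal (0.5% to 0.9%). Selection also matters little if the drug works as designed: at a true effect of 0.99 SD and no drift, the bias among continuing trials is 0.02 to 0.06 SD under the two assumed rules. The shift sizes have no source in the documents. What remains is the rate among trials that reach the comparison, and the loss of randomisation for 59% of one arm, which needs no assumed shift.

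A reader might go further and infer that the trial as planned randomises only 24 patients and is therefore underpowered. The documents do not support that. Section 5 and Number of Subjects both state 17 per group, and 24 randomised patients cannot supply 17 in each. The lower power describes only what follows if the 10 are set aside within a fixed total of 34. It is also partly built in, because the effect was solved to give exactly 80% at 17 v 17.

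**Conclusion.** The concern holds as an unresolved ambiguity with one sound reading and one damaging one. The documents do not establish that the 10 are counted; they leave it open, with section 5 leaning that way.

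If the 10 are counted, 59% of the BT arm is unrandomised and known to be on BT, and the BT-saline difference cannot be presented as a randomised comparison. That conclusion rests only on the plan's own numbers. The bias of 0.12 to 0.29 SD and the false-positive rates (about 1.7% to 10% overall, about 16% to 26% among continuing trials) are illustrations. They depend on SD 1, no drug effect, the assumed shifts and the assumed go rules.

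It must be fixed, because it decides what the trial can conclude and cannot credibly be settled once the first 10 results are known.

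**What to change.** Before the lead-in results are seen, state the following in section 5, Number of Subjects, Study Timelines, the later Procedures Involved section and Data Analysis:
- The first 10 patients are a separate, non-randomised, single-arm BT lead-in. They are excluded from the BT-saline comparison and reported separately.
- The 17 v 17 and the 80% power refer to randomised patients only, so the total is 10 + 34 = 44.

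If the overall total has to stay at 34, keep the exclusion and restate the power for the 24 randomised, with the test and effect size used: about 64% at 12 v 12 under the assumptions above.

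The cost is wording in five places. Either the total or the stated power becomes less favourable, and the 10 add no precision to the BT-saline comparison. With 44 patients, the team should also confirm the timeline, since "The study is expected to last about 1 year from the time of IRB approval to completion of all study activities". The plan gives no recruitment rate from which to judge whether that still holds.

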## **Study Timelines**

Recruitment will occur for 1 year. After interim analysis, the study will end once 34 patients are recruited. The study length for the patient is expected to be at least 3 months, with the recruitment/baseline visit and follow up visits at 3 days, 1 week, 2 weeks, 1 and 3 months from the first visit, for a total of 6 visits. The study is expected to last about 1 year from the time of IRB approval to completion of all study activities, including analysis of identifiable data.

